## **8.9. Study procedures during special circumstances**

**(Amended 9 May 2021)**

During special circumstances (e.g., COVID-19 pandemic), the specific guidance from local public health and other competent authorities regarding the protection of individuals' welfare must be applied. For the duration of such special circumstances, the following measures may be implemented for enrolled subjects:

- If the Subject eDiary device was provided to the subject, it may be returned to the site by conventional mail after the end of the relevant data collection period (Visit 6).
- Study visits may be performed at a different location\* other than the study site (e.g. at subject's home). For study visits involving blood draw, biological samples should not be collected if they cannot be processed in a timely manner or appropriately stored until the intended use.
- If despite best efforts it is not possible to collect the biological samples within the interval predefined in the protocol (see [Table 4](#)), then the interval may be extended as described below in [Table 17](#).
- If despite best efforts it is not possible to administer the dose of study intervention as defined in the protocol (see [Table 4](#)), then the interval may be extended as described below in [Table 17](#).

\* It is the investigator's responsibility to identify an alternate location. The investigator should ensure that this alternate location meets ICH GCP requirements, such as adequate facilities to perform study procedures, appropriate training of the staff and documented delegation of responsibilities in this location. This alternate location should be covered by proper insurance for the conduct of study on participants by investigator and staff at a site other than the designated study site.

In case of home visits, the study procedures should be carried out by a qualified person/s as delegated by the Principal Investigator, provided that the compliance with protocol procedures are ensured. Refer to Schedule of Activities for the schedule of visits (see [Table 3](#)).

Refer to local regulations on the conduct of clinical trials during the COVID-19 pandemic for more details.

Impact on the per protocol set for immunogenicity will be determined on a case by case basis.

**CONFIDENTIAL**205416 [MENB REC 2ND GEN-038 (V72\_72)]  
Protocol Amendment 4 Final**Table 17 Intervals between study visits during special circumstances**

Interval	Length of interval	Allowed interval (Visit window)
Visit 1 → Visit 2	30 days	23 to 58 days after vaccination at V1 (from -7 to + 28 days)
Visit 1→Visit 3	60 days	53 to 88 days after vaccination at V1 (from -7 to + 28 days)
Visit 3→Visit 4	30 days	23 to 58 days after vaccination at V3 (from -7 to + 28 days)
Visit 3→Visit 5	120 days	110 to 148 days after vaccination at V3 (from -10 to +28 days)
Visit 5→Visit 6	30 days	23 to 58 days after vaccination at V5 (from -7 to + 28 days)

**8.10. Decentralised study procedures****(Amended 9 May 2021)**

*If local regulations allow and if quality of study procedures can be maintained, participant(s) can be offered remote visits (e.g. home visits) for the collection of biological samples and/or study intervention administration. These remote visits must be performed by qualified study staff/healthcare professionals HCPs. Refer to the Schedule of Activities (Table 3) for the timing of these visits.*

*Following procedures can be performed remotely. Refer to the [Glossary of terms](#) for definitions of remote virtual visit:*

- *Biological samples may be collected remotely by qualified study staff/HCPs. Biological samples should be collected only if they can be processed in a timely manner and appropriately stored until the intended use.*
- *Administration of study intervention can be performed remotely/at participant's home by qualified study staff/HCPs if appropriate storage conditions for the study intervention can be ensured. Furthermore, appropriate medical treatment must be readily available during 30 minutes after dosing in case of anaphylaxis, syncope.*

**9. DISCONTINUATION FROM THE STUDY**

From an analysis perspective, a 'withdrawal' from the study refers to any subject who was not available for the concluding contact foreseen in the protocol.

All data and samples collected until the date of withdrawal/last contact of the subject will be used for the analysis.

A subject is considered a 'withdrawal' from the study when no study procedure has occurred, no follow-up has been performed and no further information has been collected for this subject from the date of withdrawal/last contact.

Investigators will make an attempt to contact those subjects who do not return for scheduled visits or follow-up.

**CONFIDENTIAL**205416 [MENB REC 2ND GEN-038 (V72\_72)]  
Protocol Amendment 4 Final

Primary reason for study withdrawal will be documented in the eCRF. The investigator will document whether the decision to withdraw a subject from the study was made by the subject himself/herself, by the subject's parent(s)/LAR(s), or by the investigator, as well as which of the following possible reasons was responsible for withdrawal:

- Adverse events (AEs) requiring expedited reporting (please refer to section [12.5.10.2](#) for the details)
- Unsolicited non-serious AE
- Solicited AE
- Protocol deviation
- Withdrawal by subject, not due to an AE\*
- Migrated/Moved from the study area
- Lost to follow-up
- Sponsor study termination
- Other (specify)

\*In case a subject is withdrawn from the study because he/she/the subject's parent(s)/LAR(s) has withdrawn consent, the investigator will document the reason for withdrawal of consent, if specified by the subject/subject's parent(s)/LAR(s), in the eCRF.

Subjects who are withdrawn from the study because of SAEs/AEs/pregnancy must be clearly distinguished from subjects who are withdrawn for other reasons. Investigators will follow subjects who are withdrawn from the study as result of a SAE/AE/pregnancy until resolution of the event (see Section [12.5.12](#)).

A subject will be withdrawn if the subject's treatment code is unblinded by the investigator or treating physician (Refer to Section [7.3.1](#)). The primary reason for discontinuation (the event or condition which led to the unblinding) will be recorded in the eCRF.

### **Adverse Event**

For any subject withdrawn from study participation prior to the planned Study Termination Visit, it is important to determine if an AE was associated with the reason for discontinuing the study. This AE must be identified on the AE eCRF page by indicating "Withdrawn from study due to AE". Any ongoing AEs at the time of study withdrawal must be followed until resolution or stabilisation.

Subjects who develop a SAE judged to be possibly or probably related to the study vaccine, including hypersensitivity reactions, should not receive subsequent vaccination.

**CONFIDENTIAL**205416 [MENB REC 2ND GEN-038 (V72\_72)]  
Protocol Amendment 4 Final**Death**

For any subject withdrawn from study participation due to death, this should be noted on the Study Termination eCRF page and the associated SAE that led to the death must be reported.

**Withdrawal of consent**

The subject and/or parent(s)/legal guardian(s) can withdraw consent for participation in the study at any time without penalty or loss of benefit to which the subject is otherwise entitled. Reason for early termination should be deemed as “withdrawal of consent” if the subject withdraws from participation due to a non-medical reason (i.e., reason other than AE). If the subject and/or parent(s)/legal guardian(s) intends to withdraw consent from the study, the investigator should clarify if the subject will withdraw completely from the study or if the subject will continue study participation for safety, or a subset of other study procedures. If the subject requests complete withdrawal from the study, no further study interventions will be performed with the subject.

**For sites in US:** If a subject and/or parent(s)/legal guardian(s) withdraws consent but does not revoke the The Health Insurance Portability and Accountability Act (HIPAA) authorisation, the Sponsor will have full access to the subject’s medical records, including termination visit information. If a subject and/or parent(s)/legal guardian(s) revokes only the HIPAA authorisation, the Sponsor will have full access to all of the subject’s medical records prior to the date and time of written revocation.

**Lost to Follow-Up**

Refer to Section [9.2](#).

**Administrative Reason**

Examples for subjects withdrawn from the study due to administrative reason can include: Sponsor decision to terminate the study, subject meeting a pre-specified withdrawal criterion, subject discontinuation for insurance issues, moving, no time, etc. This reason should be noted in the Study Termination eCRF page and any ongoing AEs at the time of study withdrawal must be followed until resolution/stabilisation.

If the clinical study is prematurely terminated by the Sponsor, the investigator is to promptly inform the study subjects and local EC/IRB and should assure appropriate therapy and follow-up for the subjects. All procedures and requirements pertaining to the archiving of study documents should be followed. All other study materials (study medication/vaccines, etc.) must be returned to the Sponsor.

For subjects who are withdrawn from the study due to receipt of an excluded medication/vaccination or due to significant protocol non-compliance, this reason should be noted in the Study Termination eCRF page.

**CONFIDENTIAL**205416 [MENB REC 2ND GEN-038 (V72\_72)]  
Protocol Amendment 4 Final**Protocol Deviation**

A protocol deviation is any change, divergence, or departure from the study design or procedures of a study protocol. In general, subjects associated with protocol deviations may remain in the study unless continuation in the study jeopardises the subject's health, safety, or rights.

Investigators will apply due diligence to avoid protocol deviations. Under no circumstances should the investigator contact GSK or its agents, if any, monitoring the study to request approval of a protocol deviation, as no authorised deviations are permitted. If the investigator feels a change to the protocol would improve the conduct of the study this must be considered a protocol amendment, and unless such an amendment is agreed upon by GSK and approved by the IRB/EC and health authorities it cannot be implemented.

Any subject who becomes pregnant during the study, despite the protocol requirement for adequate contraception, will not receive further vaccination but should be encouraged to continue participating in the study for safety follow-up. The site must complete a Pregnancy Report eCRF (initial report) as soon as possible after learning of pregnancy occurrence (Refer to Section 12.5.9). If the subject withdraws from the study for any of the above categories except death, the site will obtain permission from the subject to continue to remain in contact with her until the outcome of the pregnancy is known, even if the outcome is not known until after the subject reaches the end of follow-up period.

**9.1. Discontinuation of study vaccine(s)/product(s)**

A 'withdrawal' from the study vaccine(s)/product(s) refers to any subject who does not receive the complete treatment, i.e. when no further planned dose is administered from the date of withdrawal. A subject withdrawn from the study vaccine(s)/product(s) may continue further study procedures (safety or immunogenicity) if planned in the study protocol, as deemed appropriate by the investigator.

Primary reason relative to premature discontinuation of the study vaccine(s)/product(s) will be documented on the Vaccine Administration screen of the eCRF. The investigator will document whether the decision to discontinue further vaccination/treatment was made by the subject himself/herself, by the subject's parent(s)/LAR(s), or by the investigator, as well as which of the following possible reasons was responsible for withdrawal:

- Adverse event requiring expedited reporting
- Unsolicited non-serious adverse event (specify)
- Solicited adverse event
- Not willing to be vaccinated
- Other (specify).

**CONFIDENTIAL**205416 [MENB REC 2ND GEN-038 (V72\_72)]  
Protocol Amendment 4 Final**9.2. Lost to follow-up**

A subject will be considered lost to follow-up if he or she repeatedly fails to return for scheduled visits and is unable to be contacted by the study site.

The following actions must be taken if a subject fails to return to the clinic for a required study visit:

- The site must attempt to contact the subject and reschedule the missed visit as soon as possible and counsel the subject on the importance of maintaining the assigned visit schedule and ascertain whether or not the subject wishes to and/or should continue in the study.
- Before a subject is deemed lost to follow-up, the investigator or designee must make every effort to regain contact with the subject (where possible, 3 telephone calls and, if necessary, a certified letter to the subject's last known mailing address or local equivalent methods). These contact attempts should be documented in the subject's medical record.
- Should the subject continue to be unreachable, he/she will be considered to have withdrawn from the study with a primary reason of lost to follow-up. The termination date for the subject to be captured on the Study Termination eCRF page is the date of the last successful contact (clinic visit or telephone) with the subject.

**10. STATISTICAL CONSIDERATIONS****10.1. Sample size determination**

(Amended 9 May 2021)

Three thousand six hundred fifty-one (3,651) subjects are to be enrolled in the study.

[Figure 1](#) presents the study design overview with the breakdown of sample size per study arm:

- MenB\_0\_2\_6: 912 subjects
- MenB\_0\_6: 912 subjects
- ABCWY-1: 548 subjects
- ABCWY-2: 548 subjects
- ABCWY-3: 548 subjects
- ACWY: 183 subjects.

It is assumed that 25% of the subjects will drop-out and not contribute to an evaluable result. The remaining subjects who do give an evaluable result provide 90% power to reject all hypotheses for the primary objectives of rMenB+OMV NZ and 92% power to reject all hypotheses for the primary objectives of MenABCWY vaccine. Additionally, the study is powered to reject key secondary objective for three *N. meningitidis* serogroup

**CONFIDENTIAL**205416 [MENB REC 2ND GEN-038 (V72\_72)]  
Protocol Amendment 4 Final

B indicator strains (96217 (NadA), M14459 (fHbp), and *MI3520* (NHBA)) with 81% power.

[figure not shown]
An explanation of the testing strategy and hypotheses can be found in Section 10.1.1 and its sub-sections. A breakdown of the power for the individual objectives can be found in Section 10.1.2 and its sub-sections.

### 10.1.1. Hypothesis testing strategy

Multiple objectives and endpoints require type I error control. Full alpha (0.05) is split equally (alpha=0.025) between rMenB+OMV NZ objectives and MenABCWY objectives. Furthermore, within rMenB+OMV NZ, as well as within MenABCWY, objectives are tested hierarchically. If the first null hypothesis is rejected, then the testing will continue with the second hypothesis at same alpha. Same for 3rd, 4th, and so forth. Whenever a null hypothesis is not rejected, then the testing will stop.

As the comparator for MenABCWY non inferiority objective for the B component will be the selected schedule of rMenB+OMV NZ as determined in this study, the objectives of rMenB+OMV NZ will be analysed first. Additionally, if all null hypotheses related to rMenB+OMV NZ objectives will be rejected, the alpha (alpha=0.025) will be propagated to the MenABCWY part, and hypotheses related to MenABCWY objectives will be tested at full alpha (alpha=0.05). See Figure 2 for an explanation of the hierarchical testing (top to bottom, the order indicated by the arrows).

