**CONFIDENTIAL**

205416 [MENB REC 2ND GEN-038 (V72\_72)]

Protocol Amendment 4 Final

Objectives	Endpoints
	
 
The frequencies and percentages of subjects with any unsolicited AEs (including all SAEs, AEs leading to withdrawal, AESIs and medically attended AEs) during the 30 days (including the day of vaccination) following each vaccination at Day 1, Day 61 and Day 181.
 
The percentages of subjects with SAEs, AEs leading to withdrawal, AESIs and medically attended AEs throughout the study period [Month 0 to Month 12].
 

Secondary	

To demonstrate the immunological non-inferiority of the MenABCWY vaccine compared to the rMenB+OMV NZ vaccine as measured by the percentages of subjects achieving a 4-fold rise in hSBA titres against N. meningitidis serogroup B indicator strains at 1 month after the last MenABCWY vaccination (0,6-months schedule) and 1 month after the rMenB+OMV NZ vaccination (0,2,6-months or 0,6-months or 0,2-months) †
 
Criterion: Non-inferiority will be demonstrated if the LL of the 2-sided 95% CI for the group difference in percentage of subjects achieving a 4-fold rise** in hSBA titres against N. meningitidis serogroup B indicator strains is above -10%.
	
The percentages of subjects with 4-fold rise** in hSBA titres against N. meningitidis serogroup B indicator strains at 1 month after the:
 
 
last MenABCWY vaccination for the ABCWY group (pooled lots) (Day 211, Month 7), and
 
3-dose vaccination series of rMenB+OMV vaccine (Day 211, Month 7 in MenB_0_2_6 group) or 2-dose vaccination series (Day 211, Month 7 in MenB_0_6 group) or 2-dose vaccination series (Day 91, Month 3 in MenB_0_2_6 group) † relative to baseline (Day 1, Month 0).
 

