^ If the co-primary effectiveness objectives for rMenB+OMV NZ are met, then all objectives for MenABCWY will be evaluated at 95% CI. Refer to Section 10.1 for details

† If all objectives of rMenB+OMV NZ are met, the comparator will be the 0,2-months schedule. If the 0,2-months objective is not met, and the 0,6-months is met, then the 0,6-months schedule will be the comparator. If the 0,6-months is also not met, then the 0,2,6-months schedule will be the comparator.

\*For the Men A, C, W, Y evaluation, the 4-fold rise is defined as:

- a post-vaccination hSBA titre  $\geq 16$  for subjects with a pre-vaccination hSBA titre  $< 4$
- a post-vaccination hSBA titre  $\geq 4$  times the LLOQ for subjects with a pre-vaccination hSBA titre  $\geq \text{LOD}$  but  $< \text{LLOQ}$ , and
- a post-vaccination hSBA titre  $\geq 4$  times the pre-vaccination titre for subjects with a pre-vaccination hSBA titre  $\geq \text{LLOQ}$ .

\*\*For the MenB evaluation, the 4-fold rise per each indicator strain is defined as:

- a post-vaccination‡ hSBA titre  $\geq 16$  for subjects with a pre-vaccination hSBA titre  $< 4$
- a post-vaccination‡ hSBA titre  $\geq 4$  times the LLOQ for subjects with a pre-vaccination hSBA titre  $\geq \text{LOD}$  and  $< \text{LLOQ}$ , and
- a post-vaccination‡ hSBA titre  $\geq 4$  times the pre-vaccination hSBA titre for subjects with a pre-vaccination hSBA titre  $\geq \text{LLOQ}$

‡ = post-2nd vaccination for 0,6 and 0,2 schedule and post-3rd vaccination for 0,2,6 schedule).

**CONFIDENTIAL**205416 [MENB REC 2ND GEN-038 (V72\_72)]  
Protocol Amendment 4 Final

\*\*\*The primary objective of immunological NI of the MenABCWY vaccine to MenACWY will be evaluated only in subjects without a previous MenACWY vaccination (unprimed). All other primary and secondary objectives will be evaluated in subjects with and without previous MenACWY vaccination (primed/unprimed).

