**Figure 2 Hierarchical testing of hypothesis**

\* Alpha split equally between rMenB+OMV NZ and MenABCWY vaccine objectives.

If all rMenB+OMV NZ objectives are achieved, MenABCWY vaccine objectives will be tested at full alpha.

**CONFIDENTIAL**205416 [MENB REC 2ND GEN-038 (V72\_72)]  
Protocol Amendment 4 Final

\*\* If all objectives of rMenB+OMV NZ are met, the comparator will be the 0,2-months schedule. If the 0,2-months objective is not met, and the 0,6-months is met, then the 0,6-months schedule will be the comparator. If the 0,6-months is also not met, then the 0,2,6-months schedule will be the comparator.

Refer to [Glossary of terms](#) for definitions of test-based and responder-based vaccine effectiveness.

An explanation of the hypothesis testing is given in the following subsections:

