**10.1.2.11. Effectiveness (Responder-based): MenABCWY**

As the underlying assumptions for MenABCWY 0-6M is the same as MenB, see Section [10.1.2.2](#).

**CONFIDENTIAL**205416 [MENB REC 2ND GEN-038 (V72\_72)]  
Protocol Amendment 4 Final**10.1.2.12. Non inferiority of MenABCWY vs rMenB+OMV NZ measured by percentage of subjects with 4-fold rise in hSBA titres against MenB component indicator strains post 2nd dose****(Amended 9 May 2021)**

Key secondary objective is to demonstrate non inferiority of MenABCWY vs rMenB+OMV NZ measured by the percentages of subjects with 4-fold rise in hSBA titres against the *N. meningitidis* serogroup B indicator strains post 2nd dose. Six hundred twenty (620) subjects are needed to demonstrate the immunological non-inferiority of the MenABCWY vaccine compared to the rMenB+OMV NZ as measured by the percentages of subjects achieving a 4-fold rise in hSBA titres against *N. meningitidis* serogroup B indicator strains at 1 month after the last MenABCWY vaccination (0,6-months schedule) and 1 month after the MenB vaccination (0,2,6-months or 0,6-months or 0,2-months) with 81% power calculated for three strains (96217 (NadA), M14459 (fHbp), and **M13520** (NHBA)). NZ98/254 (PorA) is not powered for as the 4-fold rate for MenABCWY is predicted to be at least 10% less than the 4-fold rate for MenB.

Non-inferiority will be demonstrated if the LL of the 2-sided 97.5% CI for the group difference in percentage of subjects achieving a 4-fold rise in hSBA titres against all *N. meningitidis* serogroup B indicator strains is above -10%. [Table 23](#) presents the power to meet the objective.

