**10.3.3.11. Effectiveness (Responder-based): MenABCWY**

See Section [10.3.3.2](#)

**10.3.4. Secondary effectiveness and immunogenicity analyses****10.3.4.1. Immunological non-inferiority: MenABCWY vs. rMenB+OMV NZ**

(Amended 9 May 2021)

Analysis set: PPS will be the primary analysis population.

Statistical method: The percentages of subjects with 4-fold rise in hSBA titres against *N. meningitidis* serogroup B indicator strains (M14459, 96217, **M13520** and NZ98/254 for fHbp, NadA, NHBA and PorA P1.4 antigens, respectively) at 1 month after the last vaccination for the ABCWY group (pooled lots) (Day 211, Month 7) and 1 month after the 3-dose vaccination series (Day 211, Month 7) in MenB\_0\_2\_6 group or 2-dose vaccination series (Day 211, Month 7) in MenB\_0\_6 group or 2-dose vaccination series (Day 91, Month 3) in MenB\_0\_2\_6 group and the corresponding exact 2-sided 95% CIs based on Clopper-Pearson method will be calculated [Clopper, 1934]. The 95% CIs for the difference in percentages between ABCWY group (pooled lots) and MenB\_0\_2\_6 group and MenB\_0\_6 group will be constructed using the method of Miettinen and Nurminen [Miettinen, 1985].

Non-inferiority criterion: Non-inferiority of MenABCWY vaccine for the proportion of subjects with 4-fold rise will be demonstrated if the lower limit of the 2-sided 95% CI for the difference in percentage of subjects with 4-fold rise between the 2 groups (ABCWY group (pooled lots) – selected MenB group) is above -10%.

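### The key secondary MenB non-inferiority objective is judged on a flat 95% CI, which contradicts the 97.5% CI it was sized on and does not fit the alpha plan; no readable text places it in the testing order

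*Protocol*

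**What the plan says.** **The alpha plan (section 10.1.1).** The plan states: "Full alpha (0.05) is split equally (alpha=0.025) between rMenB+OMV NZ objectives and MenABCWY objectives". It adds that "within rMenB+OMV NZ, as well as within MenABCWY, objectives are tested hierarchically", and that "Whenever a null hypothesis is not rejected, then the testing will stop". The MenABCWY share can grow under one condition, given in the notes to Figure 2: "If all rMenB+OMV NZ objectives are achieved, MenABCWY vaccine objectives will be tested at full alpha". The footnote to Table 6 puts this in CI terms: "If the co-primary effectiveness objectives for rMenB+OMV NZ are met, then all objectives for MenABCWY will be evaluated at 95% CI". In Table 6 every CI-based MenABCWY primary criterion is a 97.5% CI carrying the caret mark that leads to that footnote.

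**The hypotheses.** Subsections 10.1.1.1 to 10.1.1.11 set out the hypotheses. All eleven belong to primary objectives.

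**The key secondary objective.** Section 10.1.2.12 says: "Key secondary objective is to demonstrate non inferiority of MenABCWY vs rMenB+OMV NZ", measured by 4-fold rise in hSBA titre against the MenB indicator strains, with a margin of -10%. It states 620 subjects and 81% power for three strains. The success rule appears at two levels:

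- Table 6, and the synopsis in the same words: "Non-inferiority will be demonstrated if the LL of the 2-sided 95% CI for the group difference in percentage of subjects achieving a 4-fold rise" is above the margin. There is no caret and no condition.
- Section 10.3.4.1: "Non-inferiority of MenABCWY vaccine for the proportion of subjects with 4-fold rise will be demonstrated if the lower limit of the 2-sided 95% CI" is above the margin. Again there is no condition.
- Section 10.1.2.12: the same rule, but on a two-sided 97.5% CI and for all indicator strains.

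**The concern.** An objective with a demonstration aim, a fixed margin, a success rule and its own power is a confirmatory claim. Section 10.1.1 itself says that multiple objectives need type I error control, and it leaves no alpha outside the two chains. A 95% CI rule with no condition therefore needs alpha that the MenABCWY chain holds only after all rMenB+OMV NZ nulls have been rejected.

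Two things are at stake. First, the protocol gives two answers to the question of when this objective is met: a lower limit that passes at 95% may fail at 97.5%. Second, with no written position, an analyst following Table 6 and section 10.3.4.1 could claim MenB non-inferiority at a level the plan has not allotted, or after the MenABCWY chain has stopped.

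**Working it through.** **1. Which CI level was the objective sized on?**

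Inputs, from section 10.1.2.12 and Table 23: margin 0.10; assumed 4-fold rise rates equal in both groups, at 80% (NadA), 60% (fHbp) and 45% (NHBA); n = 620, taken as per group; stated power 98.5%, 91.2% and 90.3%, jointly 81%.

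Formula (normal approximation, unpooled variance): SE = sqrt[2p(1-p)/n] and power = Phi(0.10/SE - z), with z = 2.241 for a 97.5% CI and 1.960 for a 95% CI. Joint power is the product over the three strains.

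| Strain | SE | 0.10/SE | Power, 97.5% CI | Power, 95% CI | Table 23 |
|---|---|---|---|---|---|
| NadA | 0.0227 | 4.402 | 98.5% | 99.3% | 98.5% |
| fHbp | 0.0278 | 3.594 | 91.2% | 94.9% | 91.2% |
| NHBA | 0.0283 | 3.539 | 90.3% | 94.3% | 90.3% |
| Joint | | | 81.1% | 88.8% | 81% |

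At 97.5% all three strains and the joint figure match. At 95% the joint figure does not. Other readings of the sample size do not rescue the 95% level: 310 per group gives 30.1% (97.5%) or 44.5% (95%), and 684 per group gives 86.4% or 92.4%. The objective was sized at alpha 0.025, which is the MenABCWY chain's own level before any propagation.

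**2. What does the 95% rule do to the alpha total?**

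Planned total: 0.025 + 0.025 = 0.05. In a gated chain, the chain's error is bounded by the largest level used in it. An ungated test adds its own level. The key secondary is counted as one joint claim.

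| Reading of the key secondary | Two-sided bound | One-sided equivalent |
|---|---|---|
| Last in the MenABCWY chain, at that chain's alpha | 0.025 + 0.025 = 0.05 | 0.025 |
| Last in the chain, always 95% CI, no propagation | 0.025 + 0.05 = 0.075 | 0.0375 |
| Ungated, 97.5% CI | 0.025 + 0.025 + 0.025 = 0.075 | 0.0375 |
| Ungated, 95% CI | 0.025 + 0.025 + 0.05 = 0.10 | 0.05 |

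These are additive bounds. If the tests were independent, the ungated 95% case would be 1 - 0.975 × 0.975 × 0.95 = 0.0969 and the gated 95% case 1 - 0.975 × 0.95 = 0.0738.

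Only the first row keeps the planned 0.05. The 95% CI is consistent with the plan in one situation: the test is gated and all rMenB+OMV NZ nulls have been rejected. Both the level and the position therefore need to be fixed.

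**The case against.** The strongest defence is that the plan may already intend the right procedure. Section 10.1.1 speaks of MenABCWY objectives tested in order, without limiting this to primary ones. The Table 6 footnote makes the 95% level conditional for all MenABCWY objectives. The sizing uses the chain's alpha. Figure 2, which carries the order of testing, is not in the text available here, and its last MenABCWY step could be this objective. Gating of secondary endpoints is also commonly detailed in an SAP.

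Much of this stands, and it limits the point. A reader might infer that the objective lies outside the hierarchy and is claimed whatever the primaries show, so that the trial's confirmatory error does exceed 0.05. The documents do not support that. No section says so, Figure 2 may say the opposite, and the excess depends on how the rule is read. A reader might also count a separate claim for each strain and arrive at a larger inflation. Section 10.1.2.12 asks for all strains. Under that rule the true error is smaller than the bounds above, and the plan's own forecast for PorA (53% against 76%, 0% power) makes a joint four-strain success very unlikely.

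What the defence does not remove is the conflict inside the protocol. Table 6, the synopsis and section 10.3.4.1 fix a 95% CI with no condition, and section 10.1.2.12 fixes 97.5%. A gate shown in Figure 2 would not cure this: a gated 95% rule without propagation still gives 0.075. Nor is it detail left for later, since the protocol itself states the success rule.

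**Conclusion.** The point holds as a contradiction in the success rule plus an unwritten position in the testing order. The key secondary criterion is stated at two CI levels, and the one in the objectives table and the analysis section is neither the level the objective was sized on nor the level the alpha plan provides without propagation. Applied literally in that case, it lifts the two-sided family-wise bound from 0.05 to 0.075 if gated after the MenABCWY primaries, or to 0.10 if ungated.

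This rests on counting the key secondary as one joint claim, on additive bounds rather than actual error rates, and on reading 620 as a per-group number. If Figure 2 already places the objective last in the MenABCWY chain, the gating part falls away and the conflict over the CI level remains. The matter should be corrected; it does not undermine the primary tests.

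**What to change.** In section 10.1.1, Table 6, the synopsis table and section 10.3.4.1 (and in Figure 2, if it does not already show this), state the key secondary hypothesis and make it the last step of the MenABCWY chain. Test it only if every MenABCWY primary null (10.1.1.7 to 10.1.1.11) is rejected, at the alpha that chain then holds: a two-sided 97.5% CI, or 95% only if all rMenB+OMV NZ nulls were rejected. Add the same condition to the 97.5% rule in section 10.1.2.12. If the chain stops earlier, report the estimates and CIs descriptively and make no non-inferiority claim.

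This restores the bound of 0.025 + 0.025 = 0.05 and matches the level behind the three-strain 81% power. It needs wording only, with no extra subjects or data. The cost is that the claim is lost if any MenABCWY primary objective fails, and the 81% becomes conditional on reaching that step.
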